4.8 OTHER ANALYSES

4.8.1 PK analyses

Plasma venglustat trough concentrations (pre dose) along with other single time point plasma concentration data will be summarized on the PK populations by dose and each analysis window (see Table 13 and Table 14) using the following descriptive statistics: mean, geometric mean, median, standard deviation, coefficient of variation, minimum, and maximum.

All concentration values below the lower limit of quantitation (LLOQ) will be treated as zero in all summary statistics excepted for the geometric mean and associated coefficient of variation for which they will be considered as missing.

Exploratory metabolite analysis may be performed on selected plasma samples. If data permit, PK parameters will be estimated for metabolites using noncompartmental methods. These will be summarized using descriptive statistics.

Plasma venglustat concentration data might be used for population PK modeling if considered necessary and the results of population PK modeling will be reported separately from the study report.

Exploratory PK analyses may be performed as deemed necessary to evaluate exposure-response relationships (in particular TKV, eGFR and safety parameters).

4.8.2 Pharmacodynamic analyses

Exploratory endpoints include change in:

- GL1 from baseline to 18 months in Stage 1 and 24 months in combined Stage 1 and Stage 2
- GM3 from baseline to 18 months in Stage 1 and 24 months in combined Stage 1 and Stage 2

As no sample tested for GM3 at the time of the study discontinuation, the analysis of GM3 will not be done.

GL1 variable will be summarized on the pharmacodynamics populations using descriptive statistics at each time point, including assessment of observed values, change and percent change from baseline.

4.8.3 Patient reported outcomes analyses

Figure 3 shows the concepts of measurement and their related PRO questionnaires used in the trial.

Figure 3 - Patient reported outcome (PRO) concepts and questionnaires

Concept	PRO questionnaire
Overall pain	BPI-SF
Overall fatigue	BFI-SF
Global impression of severity	PGIS
Global impression of change	PGIC
Health status	EQ-5D-5L
Daily symptoms of ADPKD (worst pain, worst fatigue, nocturia)	Daily diary

ADPKD = Autosomal dominant polycystic kidney disease; BFI-SF = Brief Fatigue Inventory-short form; BPI-SF = Brief Pain Inventory short-form; EQ-5D-5L = EuroQoL 5-dimension 5-level; PGIC = Patient global impression of change; PGIS = Patient global impression of severity; PRO = Patient reported outcome.

Overall pain

Overall pain will be measured using the BPI short-form (BPI-SF). Most BPI-SF items provide an 11-point numeric rating scale (NRS). Scores are by items and by dimensions; the global score ranges from 0 to 10. Lower scores indicate lower pain.

Exploratory endpoints include change in:

- Overall pain total score from baseline to 18 months in Stage 1 and 24 months in combined
 Stage 1 and Stage 2
- Pain severity score from baseline to 18 months in Stage 1 and 24 months in combined Stage 1 and Stage 2
- Pain interference score from baseline to 18 months in Stage 1 and 24 months in combined Stage 1 and Stage 2
- Treatment relief score from baseline to 18 months in Stage 1 and 24 months in combined Stage 1 and Stage 2

Overall fatigue

The Brief Fatigue Inventory-Short Form (BFI SF) will be used to measure overall fatigue. Scores are by dimension and the global score ranging from 0 to 10. Lower scores indicate lower fatigue.

Exploratory endpoints include change in:

- Overall fatigue total score from baseline to 18 months in Stage 1 and 24 months in combined Stage 1 and Stage 2
- Fatigue severity score from baseline to 18 months in Stage 1 and 24 months in combined Stage 1 and Stage 2
- Fatigue impact score from baseline to 18 months in Stage 1 and 24 months in combined Stage 1 and Stage 2

Health status

The EuroQoL 5-dimension 5-level (EQ-5D-5L) is used to assess the 5 following dimensions of health outcome: Mobility, Self-care, Usual activities, Pain/Discomfort, Anxiety/Depression, ranged from "1": no problems to "5": extreme problems. The EuroQoL-5D index utility score is calculated using the crosswalk method based on the UK value set (8).

Exploratory endpoints include change in:

- EQ-5D-5L utility score change from baseline to 18 months in Stage 1 and 24 months in combined Stage 1 and Stage 2
- Each of the EuroQol five dimensions (EQ-5D-5L) score from baseline to 18 months in Stage 1 and 24 months in combined Stage 1 and Stage 2

Both total scores and subscale scores of PROs will be calculated according to their scoring guidelines, including handling the missing items.

Daily symptoms of ADPKD

A daily diary will be included in the study to measure pain, fatigue and nocturia with a 24-hour recall. The diary will be completed for 7 days prior to baseline visit and for the specified administration period before the study visits. The diary will be comprised of 3 items plus an additional item that will direct to the medication entry log:

- A nocturia item: "Last night, how many times did you wake up because you had to urinate? (if you did not wake up, please write 0)".
- Item 3 of the BFI-SF to measure worst fatigue in the past 24 hours; "Please rate your fatigue (weariness, tiredness) by circling the one number that best describes your WORST level of fatigue in the last 24 hours". Response options are given on an 11-point NRS from 0 (No Fatigue) to 10 (As bad as you can imagine) (analyzed as secondary endpoint see Section 4.4).
- Item 3 of the BPI-SF to measure worst pain in the past 24 hours; "Please rate your pain by marking the box beside the number that best describes your pain at its worst in the last 24 hours". Response options are given on an 11 point NRS from 0 (no pain) to 10 (pain as bad as you can imagine) (analyzed as secondary endpoint see Section 4.4)
- Medication log entry item; "Have you taken any medication for your pain in the past 24 hours? Yes/No".

Daily diaries scores will be averaged over 7 consecutive assessments prior to the 1st IMP (or prior randomization for participants randomized and not exposed), Month 3 and Month 12 planned visit and over the 14 consecutive days prior to the planned Month 18 and Month 24 visits. At least 50% of the days in the observation period (ie, 4 or more of the 7 days for baseline, Month 3 and Month 12; 7 or more of the 14 days for Month 18 and Month 24) are required to calculate the average score on non-missing data (4, 5).

Exploratory endpoints include change in nocturia from baseline to 18 months in Stage 1 and 24 months in combined Stage 1 and Stage 2, based on patient reported diary.

Main analytical approach

Change from baseline to Month 18 in Stage 1 and Month 24 in combined Stage 1 and Stage 2 in pain and fatigue Item 3 are described in Section 4.4.1.1.

Each other efficacy endpoints will be summarized using descriptive statistics at each time point, including assessment of observed values, change and percent change from baseline.

In addition, any analgesic/over the counter (OTC) medication administered for pain from baseline in combined Stage 1 and Stage 2 will be summarized by study intervention group. Medication type, frequency, and dosage will be also listed.

Patient global impression of severity

The PGIS is a single item scale in which patients indicate an overall assessment of their APKD symptoms (none, mild, moderate, and severe). PGIS will be summarized and compared between venglustat 15 mg, venglustat 8 mg and placebo using descriptive statistics at each time point, including assessment of observed values and change from baseline.

Patient Global Impression of Change

The PGIC consists of one item adapted to the patient that evaluates all aspects of patients' health and assesses if there has been an improvement or decline in clinical status since they started taking the study medication (7-category scale from "very much better" to "very much worse"). PGIC will be summarized and compared between venglustat 15 mg, venglustat 8 mg and placebo using descriptive statistics at each time point.

4.8.4 Biomarker analyses

Pharmacodynamic biomarkers associated with ADPKD such as FGF23 and ADMA in plasma will be analyzed using appropriate bioanalytical platforms at the Sponsor's laboratory or at a subcontracted laboratory. Other analytes may also be assessed if available data during the course of the study suggest a relationship to disease course in ADPKD patients or to venglustat.

Exploratory endpoints include change in:

- FGF23 and ADMA from baseline to 18 months in Stage 1 and 24 months in combined Stage 1 and Stage 2
- ADMA from baseline to 18 months in Stage 1 and 24 months in combined Stage 1 and Stage 2

Each biomarker will be summarized using descriptive statistics at each time point, including assessment of observed values, change and percent change from baseline.

4.8.5 Hospitalization analyses

Number and percentage of participants with all cause hospitalization, up to Month 18 visit for Stage 1 and up to Month 24 for combined Stage 1 and Stage 2 will be summarized.

Time to first all-cause hospitalization is defined as the time from randomization to the date of hospitalization. Participants who are not hospitalized before the last contact date will be censored at the last contact date. Time to hospitalization will be analyzed using Kaplan-Meier method.

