Table 14 - Analyses window definition for PK analyses - Stage 2	53
Table 15 - Operating characteristics of the study design assuming the dose 15 mg is selected for	
Table 16 - Operating characteristics of the study design assuming the dose 8 mg is selected for	
LIST OF FIGURES	
Figure 1 - Prespecified candidate of dose-response models	21
Figure 2 - Graphical illustration of the procedure for handling multiplicity	28
Figure 3 - Patient reported outcome (PRO) concents and questionnaires	38

VERSION HISTORY

This statistical analysis plan (SAP) for study EFC15392 is based on the protocol amendment 5 dated 17-July-2020. There are no major changes to the statistical analysis features in this SAP.

The first participant was randomized in the Stage 1 population on 11-Feb-2019. This SAP is approved before the futility analysis which is planned when all participants from Stage 1 have completed the first 9 months of treatment and approximately 30% have completed 18 months of treatment with Total Kidney Volume (TKV) available (or have prematurely discontinued).

Table 1 - Major changes in statistical analysis plan

SAP Version	Approval Date	Changes	Rationale
1	19-Jan-2021	The Population without trial impact (disruption) due to COVID-19 has been defined and additional analysis performed according to this population	In order to assess the impact of the COVID19 on the study
2	22-Jun-2021	Labels of treatment group updated from GZ/SAR402671 to venglustat	Clarification
		Added definition of baseline specific to Patient symptom diaries parameters and urine osmolality (see Section 4.1 and Section 4.8.3)	Clarification
		Update of the definition the treatment emergent period for patients who participate to the long-term extension LTS15823 (see Section 4.1)	Clarification
		Update of the tertiary endpoint related to TLV to be analyzed in participants with height adjusted total liver volume [htTLV] >1 L/m instead of > 2L/m (see Section 1.2 and Section 4.5.1)	Selection of participant with htTLV >2 L/m was to strict. According to HALT publication (1) it's acceptable to consider moderate PLD as htLV >1 L/m.
		Update of tertiary endpoint related to hospitalization to analyze rate and time of all-cause hospitalization (see Section 1.2, Section 4.5.1 and Section 4.8.5)	Clarification of endpoint
		PK populations and PK data analysis time windows have been updated (see Section 3 and Section 5.4)	Correction of time points as per protocol

22-Jun-2021	
Version number:	2

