2 SAMPLE SIZE DETERMINATION

In Stage 1, approximately 240 participants will be randomized (with randomization ratio 1:1:1) to placebo (n=80) or venglustat 8 mg (n=80) or venglustat 15 mg (n=80mg).

In Stage 2, approximately 320 participants with an eGFR between 45 and 89.9 mL/min/1.73 m² at screening will be randomized (with randomization ratio 1:1) to placebo (n=160) or venglustat (n=160).

In addition, 80 participants with an eGFR between 30 and 44.9 mL/min/1.73 m² at screening will be randomized (with randomization ratio 1:1) to placebo (n=40) or venglustat (n=40). The participants from Stage 2 with an eGFR between 30 and 44.9 mL/min/1.73 m² will not be included in the primary efficacy and safety analyses populations but the data from these participants will be analyzed separately.

This sample size will provide approximately 89% power to detect a 50% reduction in annualized rate of change in TKV at end of Stage 1 and approximately 87% power to detect a 30% reduction in annualized rate of change in eGFR between venglustat and placebo at the end of Stage 2. Overall, the total sample size will provide approximately 87% power to detect an effect on both TKV and eGFR.

Sample size and power calculations were based on simulations, assuming different scenarios regarding the dose-response relationship (Section 5.6.1). SAS program is provided in (Section 5.5). The following model parameters were estimated based on available datasets from a similar participant population (participants aged 18 to 50 years with Mayo class 1C-1E and baseline eGFR from 45 to 90 mL/min/1.73 m²) in 2 historical studies (Consortium for Radiologic Imaging Studies of Polycystic Kidney Disease (CRISP) and the Polycystic Kidney Disease Treatment Network ([HALT-PKD]):

- A slope of log10(TKV) of 0.02591, 0.02832 and 0.03141 in participants from Mayo class 1C, 1D and 1E respectively (corresponding to 6.1%, 6.7% and 7.5% increase per year in TKV), resulting in average slope of 0.02764 (6.6%/year) assuming 50% of 1C, 33% of 1D and 17% of 1E.
- Standard deviation for the residual error of TKV (on the log10 scale) of 0.02566 and standard deviation for the random effect of slope of 0.01477.
- A slope of eGFR of -3.16, -3.88 and -4.69 mL/min/1.73 m² per year in participants from Mayo class 1C, 1D and 1E respectively, resulting in average slope of -3.66 mL/min/1.73 m² per year assuming 50% of 1C, 33% of 1D and 17% of 1E.

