4.5 TERTIARY/EXPLORATORY ENDPOINT(S) ANALYSIS

4.5.1 Definition of endpoint(s)

In Stage 1 and Stage 2, the following endpoints are defined as exploratory efficacy endpoints:

- Annualized rate of change in TLV based on MRI from baseline to 18 months on participants with htTLV >1 L/m
- Change in:
 - Urine osmolality from baseline to 18 months in Stage 1 and 24 months in combined Stage 1 and Stage 2 (in participants not on diuretic at baseline)
 - Nocturia from baseline to 18 months in Stage 1 and 24 months in combined Stage 1 and Stage 2, based on the daily symptom diary (see Section 4.8.3)
 - Systolic BP during the treatment emergent period (see Section 4.7.3.1)
 - Diastolic BP during the treatment emergent period (see Section 4.7.3.1)
 - Biomarkers associated with ADPKD (eg, FGF23 and ADMA) from baseline to 18 months from baseline to 18 months in Stage 1 and 24 months in combined Stage 1 and Stage 2 (see Section 4.8.4)
 - Pain (BPI), fatigue (BFI) and health status (EQ-5D-5L) from baseline to 18 months in Stage 1 and 24 months in combined Stage 1 and Stage 2 (see Section 4.8.3)
 - Glucosylceramide (GL1) and GM3 from baseline to 18 months in Stage 1 and 24 months in combined Stage 1 and Stage 2 (see Section 4.8.2)
- Type, frequency, and dosage of analgesic/over the counter (OTC) pain medication administration from baseline to 24 months (see Section 4.8.3)
- Rate of all-cause hospitalization (see Section 4.8.5)

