4.7.1 Extent of exposure

The extent of IMP exposure will be assessed by the duration of IMP exposure and compliance and summarized on the Extended combined Stage 1 and Stage 2 safety population.

In addition, summaries will be provided in the population with trial impact (disruption) due to Covid-19.

Duration of IMP exposure

Duration of IMP exposure is defined as last IMP administration date – first IMP administration date + 1 day, regardless of unplanned intermittent discontinuations. If the date of the last dose of IMP is missing, the duration of IMP will be left as missing.

Duration of IMP exposure will be summarized quantitatively and categorically:

- ≥1 day
- >1 Month
- >3 months
- ≥ 6 months
- ≥ 12 months
- \geq 15 months
- >18 months
- \geq 21 months
- >24 months

Additionally, the cumulative duration of treatment exposure (expressed in participant-years) will be provided.

Treatment compliance

A given administration will be considered noncompliant if the participant did not receive the number of days of IMP as required by the protocol. No imputation will be made for participants with missing or incomplete data.

Percentage of treatment compliance for a participant will be defined as the number of days of IMP administered divided by the total number of days that the participant was planned to take from the first administration of IMP up to the actual last administration of IMP.

Treatment compliance will be summarized quantitatively and categorically: <80%, $\ge80\%$.

Cases of overdose are reported in the adverse event (AE) e-CRF pages as Adverse Event of Special Interest (AESI) if symptomatic or AE if asymptomatic. The reported cases of overdose will be described in the AE analysis (see Section 4.7.2).

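### After the early stop, the combined-stage crude percentage hospitalised is not comparable for the 8 mg arm, and no person-time rate is defined

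*SAP*

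**What the plan says.** SAP Section 4.5.1 lists the endpoint as a rate and refers to Section 4.8.5 for its analysis. The SAP's version history (Table 1) records the version 2 change as "Update of tertiary endpoint related to hospitalization to analyze rate and time of all-cause hospitalization".

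Section 4.8.5 plans two summaries:

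- A count and percentage: "Number and percentage of participants with all cause hospitalization, up to Month 18 visit for Stage 1", continuing "up to Month 24 for combined Stage 1 and Stage 2 will be summarized".
- Time from randomisation to first hospitalisation. "Participants who are not hospitalized before the last contact date will be censored at the last contact date", and "Time to hospitalization will be analyzed using Kaplan-Meier method".

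Section 4.8.5 names no analysis population, no person-time denominator and no handling of repeat admissions. Section 4.1 says that results are presented by intervention group unless stated otherwise. Sections 1.1 and 4.9.2 record that the study was stopped after the futility analysis and that a single analysis will use whatever data are available from both stages.

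**The concern.** A percentage of participants with an event can be compared between arms only if the arms were followed for similar times. In the combined set this is doubtful for one arm. Under SAP Section 1.1, 8 mg was randomised only in Stage 1, and Stage 2 has placebo and 15 mg only. After the stop, Month 24 is a nominal limit that many participants will not have reached, and Stage 2 participants are likely to be furthest from it. The 8 mg column would then hold only Stage 1 participants, while the columns beside it would be mostly Stage 2.

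If Stage 2 follow-up is shorter, 8 mg will show a higher percentage hospitalised than placebo or 15 mg even if the drug does nothing. Anyone reading that row as a safety or benefit signal for the lower dose would be misled. SAP version 2 was written after the stop, so the imbalance was foreseeable when the summary was kept.

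**Working it through.** The documents give no hospitalisation rate, event count or power for this endpoint, so there is no planned figure to reproduce. The check asks what the crude percentages would look like if the hazard were the same in every arm.

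**Inputs from the documents**

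- Planned sizes (SAP Section 2): Stage 1, 80 per arm; Stage 2 with screening eGFR 45 to 89.9, 160 per arm. The Stage 1 share of pooled placebo or 15 mg is 80/240 = 1/3. For 8 mg it is 1.
- Stage 1 follow-up at the interim (SAP Section 4.9.2): everyone past 9 months and about 30% past 18 months, or discontinued. Ignoring discontinuation, the mean f1 lies between (0.7 × 9 + 0.3 × 18)/12 = 0.975 years and (0.7 × 18 + 0.3 × 24)/12 = 1.65 years. The midpoint is 1.31 years.
- Stage 2 follow-up: Section 4.4.2.2 says that no post-baseline MRI will be available, and Protocol Section 9.4.1 places the Stage 2 MRI at Month 18. Follow-up is therefore taken to be below about 1.5 years. No mean is given.

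**Assumptions not in the documents**

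- Constant hazard h, equal in all arms: 0.10 per year, varied from 0.05 to 0.20.
- Mean Stage 2 follow-up f2: 0.25 to 1.0 years, with 1.49 years as an extreme.

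**Formulas**

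- 8 mg: 1 − exp(−h·f1)
- Pooled placebo or 15 mg: (1/3)[1 − exp(−h·f1)] + (2/3)[1 − exp(−h·f2)]

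**Results at h = 0.10 and f1 = 1.31 years**

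| f2 (years) | 8 mg | Pooled arm | Ratio |
|---|---|---|---|
| 0.25 | 12.3% | 5.7% | 2.14 |
| 0.5 | 12.3% | 7.4% | 1.67 |
| 0.75 | 12.3% | 8.9% | 1.38 |
| 1.0 | 12.3% | 10.4% | 1.18 |

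**Range.** The ratio exceeds 1 whenever f1 exceeds f2, and it hardly depends on h. The lowest value over the grid is 0.75 (f1 = 0.975, f2 = 1.49; 9.3% against 12.3% at h = 0.10). The highest is 2.28 (f1 = 1.65, f2 = 0.25, h = 0.05; 7.9% against 3.5%).

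**Unaffected comparisons.** Placebo and 15 mg have the same planned stage mix (1/3 and 2/3), so no artefact is expected between them. Within Stage 1 the three arms were randomised concurrently 1:1:1. Had everyone been followed for the planned 24 months, both groups would give 1 − exp(−0.10 × 2) = 18.1%.

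**Effect of a person-time denominator.** Expected first events in a stage are 1 − exp(−h·f), and expected time to first event or censoring is [1 − exp(−h·f)]/h. Their ratio is h for any f and any mix of stages. With f1 = 1.31 and f2 = 0.5 years, both groups return 0.10 per participant-year.

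**The case against.** The strongest reply is that Section 4.8.5 already contains the remedy. Under non-informative censoring, Kaplan-Meier with censoring at last contact handles unequal follow-up for first events. The separate Stage 1 summary already gives a like-for-like view of 8 mg against placebo. The endpoint is exploratory and outside the multiplicity procedure in Section 4.6, and no test of it is specified. Neither document defines rate as events per person-time, so a percentage plus a time-to-event analysis is a possible reading of the change log.

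Most of this stands, and it rules out several stronger readings that a reader might infer:

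- That hospitalisation is analysed only as a crude percentage. The Kaplan-Meier analysis is in the same section.
- That the selected dose is affected. On planned sizes, 15 mg and placebo share the same stage mix.
- That the design is biased against 8 mg. Both stages were planned for 24 months, so the imbalance comes from the stop.
- That 8 mg was followed much longer as a matter of record. This is an inference. Amendment 07 (19 April 2021) opened the mGFR substudy, which needs a Month 0 measurement, to all countries shortly before the DMC review of 14 May 2021. That suggests Stage 2 was still recruiting, but no Stage 2 mean or actual enrolment is given.
- That the SAP promised to count repeat admissions. It did not.

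What the reply does not answer is that the combined percentage is still planned, by arm, with nothing to warn the reader that the 8 mg column has a different follow-up. Kaplan-Meier gives neither a rate nor a count of repeat admissions, and it does not remove the difference in stage mix.

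**Conclusion.** The point holds in a narrow form. In the combined-stage summary, the crude 8 mg percentage is not comparable with pooled placebo or 15 mg, and an endpoint called a rate has no exposure-adjusted rate defined. With the central Stage 1 follow-up and assumed Stage 2 means of 0.25 to 1.0 years, the spurious ratio is about 2.1 to 1.2. The extreme bounds of 0.75 to 2.3 show that even the direction is probable and not certain: the lower end needs mean Stage 2 follow-up near its ceiling while Stage 1 is at its minimum. The figures rest on planned sizes, no dropout, a constant equal hazard and interim-date bounds for Stage 1. No confirmatory conclusion is touched. This is a cheap improvement to a descriptive table.

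**What to change.** In Section 4.8.5, for the combined analysis:

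- Add hospitalisations per 100 participant-years by arm with a 95% CI: first events, and all events if repeat admissions are of interest.
- Use time from randomisation to last contact as the denominator, stopping at the first hospitalisation for the first-event rate. Do not borrow the Section 4.7.1 figure ("the cumulative duration of treatment exposure (expressed in participant-years) will be provided"). It measures time on study drug, whereas hospitalisations here are followed to last contact, including time off drug.
- Present combined results by stage, or restrict 8 mg comparisons to concurrent Stage 1 participants.
- Keep the Kaplan-Meier analysis and the Stage 1 summary as they are.

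The cost is one extra descriptive table. Last contact dates are already needed for the Kaplan-Meier censoring, so no new data are required.
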